#### **Study Objective s:**

Based on our pilot data we believe that the proportion of individuals classified as normotensive will be increased after 30-days of treatment with midodrine compared to those treated with placebo. We plan to classify individuals as normotensive if SBP is within the target range of 111-139 mmHg for  $\geq 50\%$  of the 24-hour observation (i.e., about 60 BP recordings) during the post-treatment period and the post-treatment relative risk of hypotension in the midodrine group versus placebo group will be assessed. Relative risk will be

determined by casting raw data into simple counts in a 2x2 contingency table, from which the proportion of cases that are classified as hypotensive in the midodrine group will be divided by the proportion of hypotensive cases in the placebo group. The 95% confidence interval for the relative risk value will be constructed, as described by Newcombe and Altman. In addition, clinical relevance will be quantified by calculating the number needed to treat (NNT) from the relative risk calculation as follows:  $NNT = 1 / (\text{hypotension rate in midodrine group} - \text{hypotension rate in placebo group})$ .

We hypothesize that, during a typical 24-hour day, the proportion of SBP observations within the target range of 111-139 mmHg will be increased after treatment with midodrine compared to placebo, after controlling for the baseline proportion. We anticipate that about >50% of the subjects randomized to midodrine will have normal 24-hour SBP after 30-days of treatment. In contrast we expect < 25% of individuals randomized to receive placebo to have normal 24-hour SBP after the 30-day intervention. If our postulated values are accurate, the relative risk for hypotension for the subjects on midodrine would be ~0.67, which represents about a 33% reduction in the rate of hypotension in subjects treated with midodrine compared to those randomized to placebo. The resulting NNT is ~ 4, which suggests that about 4 subjects with SCI would need to be treated with midodrine to normalize BP in one subject.

We will then determine the effect of increasing SBP to normal levels on the following outcome parameters:

Cerebral Blood Flow:

- Analysis of covariance (ANCOVA) will be used to determine the change in CBF at rest and during cognitive testing following randomization to midodrine versus placebo. Pre-randomization CBF will be used as the covariate. Our hypothesis is that there will be a significant increase in CBF, both at rest and during cognitive testing, after 30-days treatment with midodrine compared to placebo.

Memory and Attention Processing :

- ANCOVA will be used to determine the change in cognitive function from baseline to post-treatment following randomization to midodrine versus placebo, using the pre-randomization t-score as the covariate. Our hypothesis is that there will be a significant improvement in cognitive function in individuals treated with midodrine as assessed by standardized cognitive tests of memory and attention & processing speed compared to those randomized to placebo.

Depression, Anxiety and Fatigue :

- ANCOVA will be used to determine the change in mood and QOL score from baseline to post-treatment following randomization to midodrine versus placebo, using the pre-randomization QOL score as the covariate. Our hypothesis is that there will be a significant improvement in QOL in individuals treated with midodrine as assessed by the BPQOL compared to those randomized to placebo.

Adverse Events Reporting :

- To determine the differences in AEs reported at the end of 30-days treatment following randomization to midodrine versus placebo. Our hypothesis is that there will be an increase in mild and moderate drug-related AEs in individuals treated with midodrine compared to those on placebo. A few AE's may be expected to include supine hypertension (may not have been present prior to drug **administration**), **exacerbation of AD (elevated BPs recorded during known trigger's for AD, such as bowel care, bladder distension, transfers), pruritis, urinary retention and more severe or more frequent headaches.**

Secondary Analyses :

- Our conceptual model is that prescription medication class, use of support stockings, abdominal binders and history of TBI may function as mediator variables between SCI and the dependent variables. To explore this mediation, at a first level of analysis we will examine the bivariate relationships between the mediator and dependent variables. Second, we will build hierarchical multiple regression models in which a potential mediator variable and SCI status (dummy coded) are both forced into the model. In addition, examination of the partial correlation between SCI and dependent variables (after partialing out the effect of the mediators relative to the zero order correlation will provide insight into the effect size.

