## Research Design and Methods

We propose to determine the effects of midodrine, administered in a randomized, double blind, placebo-controlled, outpatient trial to normalize BP over a 30-day period, on CBF, cognitive function, mood and QOL. Our primary objective is to generate pilot data describing the effect size of change in CBF, cognitive test score, mood and QOL following sustained elevation in BP, to normal levels, in hypotensive individuals with SCI.

Approximately 50 subjects with SCI will be screened for study eligibility. We anticipate that approximately 40 of the subjects screened will be eligible and will undergo a 4-hour laboratory dose-effect trial. Once dose has been determined subjects will be randomized by IVAN (Interactive Touch Tone Randomization System) to receive either midodrine or placebo for the 30-day out-patient drug treatment intervention. Randomization will occur in a double-blinded manner, and individuals that use an abdominal binder regularly will be stratified equally as will those with a positive history of traumatic brain injury (TBI). Our recruitment target is 20 subjects per randomization category. We estimate approximately 10% attrition during the 30-day out-patient treatment protocol; as such, complete data will be available in ~36 subjects. Study medication and placebo will be distributed by the James J Peters VAMC Pharmacy Service. The study is proposed to be completed in two years. Total enrollment will be accomplished within 18 months of obtaining full IRB approval, which should be complete within 6 months of funding, and subject participation is estimated to last about 6-8 weeks.

**Eligibility Criteria – Inclusion Criteria:** (1) males and non pregnant females; (2) 18 – 65 years of age; (3) chronic SCI ( $\geq 1$  year post injury); (4) ability to provide informed consent; (5) laboratory or clinical evidence of hypotension (WHO criteria - SBP  $\leq 110$  mmHg in males and  $\leq 100$  mmHg in females). **Exclusion Criteria:** (1) SBP  $> 110$  mmHg for males and  $> 100$  mmHg for females (2) documented history of: (a) coronary artery disease, (b) stroke, (c) diabetes mellitus, (d) current pregnancy or lactation, (e) cardiac arrhythmias; (f) significant systemic, hepatic, cardiac or renal illness, (g) suspected malignancy, (h) neurological disease other

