than SCI; (i) history of frequent and/or severe autonomic dysreflexia (AD)\*; (j) known drug allergy to midodrine; (k) acute current illness or infection (l) psychiatric disorders and (m) substance abuse.

\*The incidence of AD is reported to be between 48-90% during rehabilitation in individuals with tetraplegia and high paraplegia (above T6), and may increase with time post-injury. However, in our review of the medical record, the diagnosis of AD was about 6% of veterans with tetraplegia and high paraplegia (T1-T6), the diagnosis of AD was less than 1% in those with lower thoracic lesions (T7 and below). Because administration of midodrine may worsen BP elevations during episodes of AD, and we cannot rely on the medical record for an accurate report of this condition, we will administer an AD questionnaire (Appendix 4) to all participants, any potential subject with frequent (3+ episodes/week) or severe (BP elevation  $\geq$  150/95 mmHg and/or self-reported adverse symptomology) episodes of AD will be excluded. To evaluate the impact of midodrine on BP elevations during AD, eligible subjects will be sent home with the same survey, modified to include: subject number, the date and the BP readings.

**Screening Visit** – Individuals with SCI will be approached by investigators and asked to provide informed consent to participate in the Screening Phase to determine eligibility. Any subject taking a vasoconstrictor agent will be asked to stop these medications 2 days or 5 half lives (whichever is longer) prior to the screening visit. The screening assessments will include: medical intake information (Appendix 5), medical history (Appendix 6), physical examination, American Spinal Cord Injury Impairment Scale (AIS) classification, clinical symptoms survey for OH and BP monitoring. The BP monitoring will include brachial manual assessments for 10 minutes in the seated and 10 minutes in the supine position and will be recorded each minute. Individuals will be eligible to participate if the average seated or supine recordings meets the WHO criteria and there is no evidence of sustained elevation in BP  $>135/85$  mmHg. This visit will take about 2 hours.

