**Pre- and Post -Treatment Visits** – Within 1 week of determining the appropriate dose of midodrine for each subject, eligible participants will return to the laboratory for pre-randomization testing including: (1) laboratory BP and heart rate (HR) assessments, (2) CBF measurement at rest and during cognitive testing, (3) cognitive testing, (4) mood and QOL surveys, (5) 24-hour ambulatory BP monitoring and (6) 24-urine volume. Subjects will arrive at the laboratory between 10AM and 1PM after a 4 hour fast, and having avoided alcohol, caffeine, and nicotine for 12-hours. Subjects will remain in their wheelchair for instrumentation, which will include: 1) electrocardiogram (ECG): three surface electrodes will be applied to the chest for continuous 3-lead recording of heart rate (HR); 2) brachial BP: will be monitored using a manual sphygmomanometer and finger arteriolar beat-to-beat BP will be recorded using a photoplethysmograph placed around the middle and index fingers of the left hand; 3) CBF: will be monitored and recorded from the right and left middle cerebral artery (MCA) using transcranial Doppler ultrasound technology. Subjects will remain in the seated position for 30 minutes of baseline (BL) data collection; HR, BP, CBF will be monitored continuously for 5-minutes at 0, 10 and 20 minutes, brachial BP will be monitored and recorded at 30-second intervals during each of the 5-minute data collections periods. After the BL assessments subjects will be asked to participate in a complete neuropsychological battery (Appendix 7) which will include assessments of: pre-morbid intellectual abilities, attention & concentration, information processing, memory, and executive control. The NP battery will take

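### The normotensive class, relative risk and NNT ignore the baseline 24-hour recording, so some subjects already in range before randomisation can be read as having had their BP normalised

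*Combined protocol and SAP*

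**What the plan says.** **Entry.** Under Research Design and Methods, hypotension means SBP of at most 110 mmHg in men and 100 mmHg in women. The Screening Visit paragraph specifies "The BP monitoring will include brachial manual assessments for 10 minutes in the seated and 10 minutes in the supine position", read every minute, and a subject is eligible if the "average seated or supine recordings meets the WHO criteria". Either position is enough, at a single visit.

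**Baseline 24-hour recording.** The Pre- and Post-Treatment Visits paragraph lists "5) 24-hour ambulatory BP monitoring" among the pre-randomisation tests. No eligibility rule uses it.

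**Outcome.** In the Study Objectives: "We plan to classify individuals as normotensive if SBP is within the target range of 111-139 mmHg for" at least 50% "of the 24-hour observation (i.e., about 60 BP recordings) during the post-treatment period". The range is the same for both sexes. The relative risk of hypotension is a ratio of raw proportions in a 2x2 table, and the NNT is the reciprocal of their difference. The NNT of about 4 is then read to mean that "about 4 subjects with SCI would need to be treated with midodrine to normalize BP in one subject".

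**Continuous version.** The next hypothesis in that section compares the proportion of readings in range between arms with adjustment for its baseline value. The adjustment is not carried over to the 2x2 table, relative risk or NNT.

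**The concern.** Normalising BP implies a change of state. The response rule looks only at the state after treatment. It asks for no minimum rise and no evidence that the subject failed the same rule beforehand. Meeting the entry criterion does not supply that evidence, because a short laboratory average and a 60-reading 24-hour rule are different measurements. For men the two cut-offs also abut (110 and 111 mmHg); for women there are 11 mmHg between them.

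The study exists to supply data that will justify a larger trial. Its anticipated rates of normal 24-hour SBP, above 50% on midodrine and below 25% on placebo, are likely to be carried forward as the share of hypotensive subjects whose BP was normalised. They are a mixture of conversions and of subjects who were in range at the start.

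**Working it through.** **1. The plan's own figures.** With normotensive rates of 0.50 and 0.25, hypotension rates are 0.50 and 0.75. Relative risk = 0.50/0.75 = 0.67. NNT = 1/|0.50 − 0.75| = 4 (the formula as written gives −4). Completers: 40 × 0.9 = 36, or 18 per arm. All agree with the plan.

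**2. What those figures would mean as conversion.** Let q be the share already normotensive at baseline, equal in both arms, and assume these subjects stay normotensive. Conversion rates among the rest are (0.50 − q)/(1 − q) and (0.25 − q)/(1 − q). The documents do not give q; under this assumption it cannot exceed the 25% placebo rate.

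| q | Midodrine | Placebo | Relative risk | NNT |
|---|---|---|---|---|
| 0 | 50.0% | 25.0% | 0.667 | 4.0 |
| 0.05 | 47.4% | 21.1% | 0.667 | 3.8 |
| 0.10 | 44.4% | 16.7% | 0.667 | 3.6 |
| 0.20 | 37.5% | 6.3% | 0.667 | 3.2 |
| 0.25 | 33.3% | 0% | 0.667 | 3.0 |

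The within-arm rates move most, the relative risk not at all, and the NNT modestly.

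**3. How large q might be.** Simulation for the male cut-off. Inputs from the Preliminary Studies: SBP 100 ± 20 mmHg (the SCI group in the cognitive study) or 90 ± 12 mmHg (the 14 subjects tested on midodrine). Assumed: visit-to-visit SD 6-10 mmHg, within-day SD 15 mmHg, and a 24-hour mean 0, 5 or 10 mmHg above the laboratory level. Subjects enter on one rounded average of at most 110 mmHg.

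The Dose Determination Visit also excludes anyone with two or more consecutive readings above 135/85 mmHg on open-label midodrine, which tends to remove men with higher underlying SBP. It was modelled on SBP at 10 mg only, with the reported mean rise of 119 − 90 = 29 mmHg, an assumed between-subject SD of 10 and reading SD of 8 mmHg.

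| Visit SD, offset (mmHg) | 100 ± 20: without / with exclusion | 90 ± 12: without / with exclusion |
|---|---|---|
| 6, 0 | 8% / 3% | 3% / 1% |
| 8, 5 | 17% / 8% | 9% / 5% |
| 10, 10 | 27% / 17% | 19% / 13% |

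Of 36 completers, 1-17% is about 0 to 6 subjects (0.01 × 36 = 0.4; 0.17 × 36 = 6.1), and 27% is about 10. Letting either position qualify raises the share somewhat: in a simpler variant with no offset and no exclusion, from 5.0% to 8.0% (100 ± 20, visit SD 8).

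**4. Chance imbalance.** The SD of the arm difference in baseline class is √(2q(1 − q)/18): 9 points at q = 0.08 and 15 points at q = 0.29. Only part reaches the outcome. With an assumed 15 mmHg rise and no dose exclusion, baseline-normotensive subjects differ from the others by 0.2-0.55 in post-treatment response probability, which leaves about 4-5 points. The standard error of the planned difference is √((0.50 × 0.50 + 0.25 × 0.75)/18) = 15.6 points. Removing 4-5 points would bring it to roughly √(15.6² − 4²) = 15.1 or √(15.6² − 5²) = 14.8. The gain is real but modest.

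**The case against.** The strongest reply is that the comparison is randomised. Already-normotensive subjects and regression to the mean fall in both arms, the relative risk hardly moves, and the planned 95% confidence interval already covers chance imbalance. In the table of step 2 the stated NNT is, if anything, conservative. All of this stands, and it limits the point to interpretation and precision.

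Three stronger readings are tempting, and the documents do not support them.

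- A reader might infer that there is no baseline 24-hour check. The recording is scheduled, and the continuous form of the same outcome is adjusted for it. What is missing is its use in the binary analysis.
- A reader might infer from the abutting male cut-offs that a 1 mmHg rise counts as response. The rule requires at least half of about 60 readings to lie in range, and for women the cut-offs do not abut.
- A reader might infer a bias in favour of midodrine. Nothing in the design produces one.

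It is also fair to say that the upper figures need a 24-hour offset that no section reports, and that 100 ± 20 mmHg describes an SCI group of whom only 62% were hypotensive. The 90 ± 12 mmHg group is nearer to the trial population. Finally, counting conversions does not remove regression to the mean: with no treatment effect, 5-17% of those not normotensive at baseline still convert in the 100 ± 20 case without the dose-visit exclusion.

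**Conclusion.** The point holds in a limited form. The binary classification, relative risk and NNT use post-treatment counts alone, while the plan adjusts the continuous version of the same outcome for baseline. A subject who already meets the 50% rule before randomisation can therefore be counted when the NNT is read as BP normalised.

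The share affected is roughly 1-17% of entrants with the dose-visit exclusion modelled, and up to about 27% without it and with an assumed 10 mmHg offset. These figures use the male cut-off and rest on assumed SDs; the structural gap does not depend on them. The between-arm comparison is protected by randomisation, and the average relative risk and NNT shift little. The consequence is that the anticipated rates of above 50% and below 25% cannot be taken as conversion rates, and that some precision is given up in a trial of about 18 per arm.

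**What to change.** In the Study Objectives:

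1. Apply the same 50% rule to the baseline 24-hour recording, and report the number already normotensive in each arm.
2. Estimate the all-randomised relative risk and risk difference, and hence the NNT, adjusted for the baseline 24-hour proportion or stratified by baseline class (Mantel-Haenszel). If very few subjects are normotensive at baseline, that stratum may hold subjects from one arm only and contribute nothing; adjustment for the proportion avoids this.
3. Report, as a supporting analysis, conversion rates among subjects not normotensive at baseline. This subset is fixed before randomisation, so the comparison stays randomised.
4. Use the word normalise, and the expectations of above 50% and below 25%, only for conversion; otherwise reword them as normotensive after treatment.

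The cost is a wording change and slightly more analysis, with no new visit or measurement. The denominator for conversion is smaller and the midodrine proportion will look less favourable. Conversion judged on one noisy recording still contains regression to the mean, so each rate must be read against placebo.

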**Dose Determination Visit** – The dose determination visit will be scheduled to begin no less than 2 days and no more than 14 days after completion of the screening visit. Our preliminary data suggest that midodrine 10 mg normalized seated SBP during a 4-hour laboratory observation in 55% of the patients with SCI tested. Therefore, it is anticipated that the 10 mg dose of midodrine will be adequate to normalize seated BP in about half of our sample. However, we appreciate that some subjects with SCI will not respond adequately to 10 mg dose (our preliminary data suggest that 28% may require a higher dose), and others may have a hypertensive response ( $>139$  mmHg: 17%, based on preliminary evidence). Eligible participants will be administered midodrine 10 mg, open-label, and BP will be monitored for 4-hours; individuals with an average 4-hour seated SBP between 111-135 mmHg will be randomized to receive 10 mg midodrine (or placebo) during the Treatment Phase. However in those with inadequate responses to 10 mg, a second open-label trial will be carried out to determine 4-hour seated SBP responses at a higher dose (15 mg) for individuals with an average SBP  $\leq$  110 mmHg, and at a lower dose (5 mg) for those with an average SBP  $> 135$  mmHg. Individuals that respond to midodrine, at any of the doses tested, with two or more consecutive BP observations of  $>135/85$  mmHg, will be excluded from the treatment phase of the investigation. Brachial BP will be recorded at 15 minute intervals and these visits will take about 5 hours.

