about 60 minutes to complete and HR, BP, and CBF will be monitored and recorded during this testing. After the NP battery is complete, subjects will be asked to answer questions related to how BPD impacts their mood and QOL (Appendix 8); these short form questionnaires were developed for use in the SCI population and will take about 15-minutes to complete. In addition, to scales developed for use in the SCI population, because fatigue was ranked highest in terms of the adverse impact of hypotension on QOL by subjects with SCI from our focus group sessions (Figure 4), we will assess fatigue specifically using the PROMIS short form and the fatigue severity scale (Appendix 8). Finally, subjects will be equipped with a 24-hour BP monitor, and will be sent home with a log to record their activities of daily living (ADL) in association with the BP recordings (Appendix 9). In addition, subjects will be sent home with a 24-hour urine collection contained and will be asked to empty their leg bag, or to urinate into this contained at each voiding for a 24-hour period to assess hydration status. Post-randomization testing will be scheduled for approximately  $30\pm3$  days after randomization and, prior to returning to the laboratory, subjects will be asked to take their morning dose of the study medication. These visits will take about 4 hours.

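### The 24-hour blood pressure rule and its two-category table do not separate readings below 111 mmHg from readings above 139 mmHg, so the normotensive proportion, relative risk and NNT can be misclassified in either direction

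*Combined protocol and SAP*

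**What the plan says.** All places are in the combined protocol and SAP.

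- **Study Objectives, responder rule.** "We plan to classify individuals as normotensive if SBP is within the target range of 111-139 mmHg for" at least 50% "of the 24-hour observation (i.e., about 60 BP recordings) during the post-treatment period". The rule is systolic only and has no separate limit on readings above the range.
- **Study Objectives, responder analysis.** The relative risk of hypotension is "determined by casting raw data into simple counts in a 2x2 contingency table". The plan expects a relative risk of about 0.67 and an NNT of about 4.
- **Study Objectives, second analysis.** The proportion of systolic readings inside 111-139 mmHg is compared between arms, controlling for the baseline proportion.
- **Adverse Events Reporting.** Adverse events are compared by arm. "A few AE's may be expected to include supine hypertension (may not have been present prior to drug" administration), and elevated pressures during triggers of autonomic dysreflexia are also named. No threshold is given, and no link to the 24-hour recording.
- **Pre- and Post-Treatment Visits.** At each of these visits "subjects will be equipped with a 24-hour BP monitor, and will be sent home with a log to record their activities of daily living (ADL").
- **Dose Determination Visit.** Subjects who respond to open-label drug "with two or more consecutive BP observations of $>135/85$ mmHg, will be excluded from the treatment phase". A diastolic limit is therefore used before randomisation.

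**The concern.** Midodrine raises blood pressure, and the plan itself expects some supine hypertension. An outcome for such a drug should distinguish pressure that is still too low from pressure that has become too high. Here both are simply out of range. A reading of 100 and one of 160 have the same effect on the in-range proportion, and the table has no cell for a subject whose pressure is mostly high.

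Two things are at stake. First, the relative risk is described as a risk of hypotension and the NNT as the number treated to normalise one subject, and neither may mean that. Second, Preliminary Studies and Data and Statistical Analysis say the results are meant to support a larger trial. That trial's planners would want to know how much time treated subjects spend above range, particularly at night. Under Treatment Phase, home readings are taken at dosing and one hour later, with doses at about 8 am, noon and 4 pm, so the 24-hour monitor is the only scheduled outcome measure that covers the night.

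**Working it through.** **1. Reproduce the plan's figures.** Inputs from Study Objectives: "We anticipate that about >50% of the subjects randomized to midodrine will have normal 24-hour SBP after 30-days of treatment" (0.50 used), and fewer than "25% of individuals randomized to receive placebo to have normal 24-hour SBP after the 30-day intervention" (0.25 used).

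- Not normotensive: midodrine 1 − 0.50 = 0.50; placebo 1 − 0.25 = 0.75.
- Relative risk = 0.50/0.75 = 0.67, as stated.
- The printed NNT formula (midodrine minus placebo) gives 1/(0.50 − 0.75) = −4. The stated 4 is its absolute value.

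These figures are obtained only if hypotensive means not normotensive, so a subject who is mostly above 139 falls in the hypotensive cell.

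**2. What the rule allows.** With 60 readings, 30 in range is enough. The other 30 may all exceed 139, which is about 12 hours if readings are evenly spaced. If about 60 is instead the 50% mark of 120 readings, the share is the same. Example: half at 125 and half at 160 gives a mean of (125 + 160)/2 = 142.5 mmHg, above the target range, and the subject is scored normotensive. With 31 of 60 above 139, the same subject is scored hypotensive.

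**3. Effect on the results, in each direction.** The shares below are assumptions; the documents give none. Placebo is held at 25% normotensive.

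*(a) A share f of midodrine subjects scored normotensive have enough high readings to be taken out of that group.* Normotensive proportion = 0.50(1 − f).

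| f | Normotensive | RR of not being normotensive | NNT to normalise |
|---|---|---|---|
| 0 | 50% | 0.67 | 4.0 |
| 10% | 45% | 0.55/0.75 = 0.73 | 1/0.20 = 5.0 |
| 25% | 37.5% | 0.625/0.75 = 0.83 | 1/0.125 = 8.0 |
| 50% | 25% | 0.75/0.75 = 1.00 | no difference |

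*(b) A share g of midodrine subjects scored hypotensive are in fact mostly high.* Hypotensive proportion = 0.50(1 − g).

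| g | Hypotensive | RR of hypotension | NNT to avoid hypotension |
|---|---|---|---|
| 0 | 50% | 0.67 | 4.0 |
| 10% | 45% | 0.45/0.75 = 0.60 | 1/0.30 = 3.3 |
| 25% | 37.5% | 0.375/0.75 = 0.50 | 1/0.375 = 2.7 |
| 50% | 25% | 0.25/0.75 = 0.33 | 1/0.50 = 2.0 |

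In (a) the plan's table flatters midodrine; in (b) it understates the effect on hypotension. The tables answer different questions, which the plan's single table merges.

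**4. How common might high readings be?** The documents give no within-subject SD and no overnight data. Assume normally distributed readings.

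- At the plan's own post-midodrine seated systolic mean of 119 mmHg (the preliminary midodrine study, a 4-hour average after 10 mg), the share above 139 is 1 − Φ((139 − 119)/SD): 2%, 9% and 16% for SD 10, 15 and 20.
- At a 24-hour mean of 135, a chosen case, it is 34% for SD 10 and 39% for SD 15, with 65% and 55% in range. At mean 130 and SD 20 it is 33%, with 50% in range. All three would be scored normotensive.

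The second set describes people whom the dose visit would often remove. With 16 independent readings (4 hours at 15-minute intervals), the chance of two consecutive systolic readings above 135 is about 96% at a seated mean of 135, and 71-87% at a mean of 130 (SD 10-20).

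**The case against.** A reader might infer that drug-induced hypertension is reported as treatment success, that no analysis counts it, and that the results are therefore biased towards midodrine. The documents do not support this.

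- Adverse events are compared by arm, and those named include supine hypertension and elevated recorded pressures during dysreflexia. The note to the eligibility criteria also sends subjects home with a dysreflexia survey that includes BP readings, in order to evaluate midodrine's effect on those episodes.
- No single reading above 139 counts as a success. Each lowers the in-range proportion, and a subject with mostly high readings counts as a failure.
- The dose-visit exclusion and the daily review of home readings for hypertensive episodes make high readings less likely, so illustrations of 33-39% overstate what to expect by day.

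All of this stands. What it does not answer is narrower. The exclusion rests on four seated hours before randomisation, not on 24 hours under three daily doses. The home review is monitoring, with no definition of an episode and no analysis attached. The adverse-event comparison has no threshold and no link to the 24-hour recording, so night-time elevation without symptoms may not be counted. None of these safeguards shows whether out-of-range 24-hour readings were low or high.

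**Conclusion.** The concern holds in its limited form. The 50% rule and the two-category table merge low and high readings: up to half above 139 can be scored normotensive, and more than half is scored hypotensive. The second statement rests on reading hypotensive as not normotensive, which the plan's 0.67 requires. The normotensive proportion, relative risk and NNT may be wrong in either direction, and the net direction is unknown. If a quarter of the relevant midodrine cell were affected (an assumption), the NNT to normalise would be 8.0 rather than 4, or the relative risk of hypotension 0.50 rather than 0.67.

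No analysis of above-range or diastolic 24-hour readings is specified. How often high readings occur cannot be told from the documents. The safeguards lower that frequency but do not report it. This should be corrected, but it does not undermine the trial.

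**What to change.** **In Study Objectives:**

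- Classify 24-hour systolic readings as below, within or above the target range, and report the three proportions by arm before and after treatment.
- For the relative risk and NNT, count a subject as hypotensive only on the basis of readings below 111. Show subjects with predominantly high readings separately, and state in advance where those with no predominant class go.
- Report by arm how many normotensive subjects have readings above range, and what share of their readings that is.

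**In Adverse Events Reporting:** add a descriptive by-arm summary of high systolic readings and, where the monitor stores them, diastolic readings from the 24-hour recording. Set the pre-randomisation recording alongside, so that new elevation can be told from existing elevation. Split by sleep or supine period if the activity log allows it; that form is in an appendix not available here. Place the summary beside the NNT. With about 36 completers, description is enough.

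**Reconcile the upper limits:** the Screening Visit and the dose-visit rules use 135 mmHg; Preliminary Studies, the Dose Determination Visit's description of a hypertensive response, and Study Objectives use 139. The sponsor must reconcile these passages.

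**Cost:** a few sentences, one more table, and possibly a less favourable normotensive proportion. Only the analysis changes, not dosing or management.
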